---

## DOCUMENT HISTORY

Version Date	Modified By	Summary of Changes
Draft / 07 Oct 2013		Draft 1
Draft / 16 Oct 2013		Draft 2: incorporated PrECOG comments for Draft 1
Draft / 28 Feb 2014		Draft 3: incorporated PrECOG comments for Draft 2
Final / 24 Mar 2014		Final: incorporated PrECOG comments for Draft 3

## 1. LIST OF ABBREVIATIONS

Abbreviation or special term	Explanation
AE(s)	Adverse Events(s)
SAP	Statistical Analysis Plan
CSR	Clinical Study Report
AI	Aromatase Inhibitor
ITT	Intention-to-Treat
QDS	Quality Data Services
QD	Once Daily
CTCAE	The CTEP Common Terminology Criteria for Adverse Events (CTCAE)
PFS	progression-free survival
RECIST	Response Evaluation Criteria in Solid Tumors
CBC	Complete Blood Count
CBR	Clinical Benefit Rate
CR	Complete Response
SD	Stable Disease
PR	Partial Response
PD	Progressive Disease
CSR	clinical study report
WHO- DD	World Health Organization Drug Dictionary
TEAEs	Treatment-emergent AEs
MedDRA	Medical Dictionary for Regulatory Activities
ICH	International Conference on Harmonization
US	United States

## **2. INTRODUCTION**

### **2.1. Objective of the Abbreviated Statistical Analysis Plan**

This abbreviated statistical analysis plan (SAP) describes the planned analysis of the safety and efficacy data from the study to be prepared for a publication based on an outline provided by sponsor (Appendix 1). A detailed description of the planned tables, figures and listings (TFLs) to be prepared for the publication is provided in the accompanying TFL template document.

The intent of this document is to provide guidance for the analysis of data related to safety and efficacy to describe any applicable statistical procedures. In general, the analyses come directly from the protocol, unless they have been modified by agreement between the Sponsor and Quality Data Services, Inc. (QDS). A limited amount of information concerning this study (e.g., objectives, study design, treatment schedule, variables and endpoints) is summarized to help the reader interpret the accompanying TFL templates. This abbreviated SAP includes details about the variables and endpoints considered for the publication. The SAP also includes clarifications for analysis population (changes from protocol specified definitions), additional endpoints and sensitivity analyses not specified in the protocol but required for the publication. Attached signatures indicate approval of the statistical analysis sections of the SAP, as well as accompanying TFL templates. These sections must be agreed upon prior to database lock. Any revisions to statistical analyses required for the publication will be document in SAP Amendment (s). Any revisions to planned TFLs which do not require revisions to SAP will be documented in a Note to SAP.

## **3. STUDY OBJECTIVES**

### **3.1. Primary Objective**

To assess progression-free survival in post-menopausal patients with hormone-receptor positive metastatic breast cancer that is resistant to aromatase inhibitor (AI) therapy treated with fulvestrant and everolimus compared to fulvestrant alone.

[figure not shown]
### **3.2. Secondary Objectives**

To describe the safety profile, objective response rate, time to progression and overall survival in post-menopausal patients with hormone-receptor positive metastatic breast cancer that is resistant to aromatase inhibitor (AI) therapy treated with fulvestrant and everolimus compared to fulvestrant alone

## 4. STUDY DESIGN

### 4.1. General Study Design and Plan

This is a randomized, double-blind, placebo controlled Phase II study. Approximately 130 subjects will be enrolled at 25 centers within the US. Subjects will be randomized (1:1) to receive everolimus or placebo after consideration of stratification factors of performance status (0 vs.1), measurable disease (with or without non-measurable) vs. non-measurable disease, and prior chemotherapy for metastatic disease vs. no prior chemotherapy. The treatment plan is defined below.

Note: 1 cycle = 28 days

### 4.2. Study Population

Subjects enrolled in the study must be postmenopausal and have stage IV disease or inoperable locally advanced disease. They must have ER and/or PR-positive disease as determined by their local pathology or reference laboratory by ASCO-CAP criteria. Tumors must be HER-2/neu negative or equivocal by standard ICH/FISH or ICH/CISH methodologies by ASCO-CAP criteria. Subjects must be Aromatase Inhibitor resistant, defined as:

- relapsed while receiving adjuvant therapy with an aromatase inhibitor (anastrozole, letrozole, or exemestane) or,
- progressive disease while receiving an aromatase inhibitor for metastatic disease

### 4.3. Treatment Administration and Duration of Therapy

Subjects must not start protocol treatment prior to randomization. Treatment is to begin within 7 working days of randomization, and includes two phases: induction phase and continuation phase.

During the Induction Phase, subjects will receive:

- fulvestrant 500 mg IM (two-250 mg injections per dose) on day 1 & 15 of Cycle 1, then 500 mg IM (two-250 mg injections) on day 1 of all subsequent cycles (every 28 days) plus everolimus 10 mg (two- 5 mg tablets) PO daily, OR
- fulvestrant 500 mg IM (two-250 mg injections per dose) on day 1 & 15 of Cycle 1, then 500 mg IM (two-250 mg injections) on day 1 of all subsequent cycles (every 28 days) plus placebo two tablets PO daily

(as randomized).

Subjects will be treated for a maximum of 12 cycles with fulvestrant plus everolimus/placebo during the Induction Phase. Induction treatment continues until there is evidence of progressive disease or unacceptable toxicity for a maximum of 12 cycles (as defined in Protocol Section 5.6). Subjects with no evidence of progressive disease who remain on study **after completing** 12 cycles of the Induction Phase are unblinded and proceed to the Continuation Phase. Subjects in the Continuation Phase will continue to receive fulvestrant alone (if originally randomized to placebo) **or** in combination with everolimus (if originally randomized to everolimus) until disease progression or unacceptable toxicity. Subjects in both the Induction and Continuation Phases will have tumor measurements performed every 12 weeks (+/- 1 week).

Protocol therapy will be discontinued for progressive disease at any time. Subjects are free to halt therapy at their request. Treatment may be discontinued if intercurrent co-morbidities occur, which, in the opinion of the treating physician, would preclude safe administration of study drugs.

Subjects who discontinue everolimus/placebo because of suspected everolimus-associated toxicity should continue treatment with fulvestrant alone until disease progression. In unusual circumstances where fulvestrant must be discontinued prior to disease progression due to intolerable fulvestrant-associated toxicity, the medical monitor should be contacted. All subjects who have discontinued protocol therapy will be followed for survival and for progression, even if protocol therapy was discontinued because of toxicity or for other reasons. All surviving subjects who have discontinued induction protocol therapy (fulvestrant and everolimus/placebo) for any reason will be followed for 30 days for study drug related (fulvestrant and/or everolimus/placebo) toxicities to  $\leq$  grade 1 (or if  $>$ grade 1, event must be permanent and stable).

#### **4.4. Dose Modifications and Toxicity Management**

Dose modifications for all drugs will be made using the general guidelines included in Protocol Section 5 (Tables 5-0, 5-1 and 5-2) and summarized below:

- All dose reductions are permanent. Fulvestrant will not be dose reduced.
- Regardless of the reason for holding any study drug treatment, the maximum allowable length of treatment interruption is  $\leq$  3 weeks. If the delivery of any study drug due to toxicity is delayed for more than 3 weeks, that drug should be permanently discontinued.
- No more than 2 dose reductions for everolimus/placebo will be allowed. Further need for dose reduction will result in discontinuation of that drug.
- If dose is delayed due to toxicity, labs/toxicity should be reevaluated at least weekly until recovery to treatment levels, or as indicated in the dose modification tables.
- Subjects who discontinue everolimus/placebo because of suspected everolimus-associated toxicity should continue treatment with fulvestrant alone until disease progression.
- In unusual circumstances where fulvestrant must be discontinued prior to disease progression due to intolerable fulvestrant-associated toxicity, the Medical Monitor should be contacted.

All toxicities will be graded according to the National Cancer Institute Common Terminology Criteria for Adverse Events (CTCAE), Version 4.0.

Toxicity management is defined in Section 5 of the protocol.

#### **4.5. Withdrawal of Subjects from Study**

Subjects are to be discontinued from study therapy and be withdrawn from the study for the following reasons:

- Withdrawal of the subject's consent (subject's decision to withdraw for any reason)
- Termination of the study by PrECOG
- Any clinical adverse event, laboratory abnormality or intercurrent illness which, in the opinion of the investigator, indicates that continued participation in the study is not in the best interest of the subject
- Inability to comply with protocol
- Discretion of the investigator
- Disease progression (subject will be followed for survival)

#### **4.6. Study Schedule of Assessments**

Study schedule of assessments is included in Appendix 2.

## 5. MEASUREMENT OF EFFECT

### 5.1. Evaluation of disease

For the purposes of this study, subjects should be re-evaluated for response every 12 weeks, +/- 1 week. All baseline evaluations should be performed as closely as possible to the beginning of treatment and never more than four weeks before randomization.

Response and progression are to be evaluated using the revised Response Evaluation Criteria in Solid Tumors (RECIST) guideline (Version 1.1). For measurable disease, changes in the sums of the longest diameters (unidimensional measurement) of the tumor lesions and the shortest diameters in the case of malignant lymph nodes are used in the RECIST criteria. For subjects without measurable disease, disappearance of disease, unequivocal progression, or the absence of either will be used to assess response. Further details and methods of evaluation of disease are included in Protocol Sections 6.1.2-6.1.3 and in SAP Appendix 3.

### 5.2. Response Criteria

Details about Response Criteria for target, non-target and new lesions are included in Protocol Sections 6.1.4.1, 6.4.1.2, 6.4.1.3, and in SAP Appendix 4.

The best overall response is the best response recorded from the start of the treatment until disease progression/recurrence (taking as reference for progressive disease the smallest measurements recorded since the treatment started). Since response is not the primary endpoint, no confirmation of response is required in this study. See Protocol Section 6.1.4.4 and SAP Appendix 5.

### 5.3. Efficacy Measurements Definitions

Efficacy measurements include progression-free survival (PFS), overall survival, and time to progression, objective response rate, clinical benefit rate (CBR), duration of overall response (CR), duration of overall CR, and duration of stable response.

Progression-free survival (PFS) is defined as the duration of time from time of randomization to time of progression or death, whichever occurs first. A subject who has neither progressed nor died will be censored on the date of last tumor assessment.

Overall Survival (OS) is defined as the time from randomization until death or censored at the date of last follow-up.

Time-to-progression (TTP) is defined as the time from randomization until progression of the disease. Patients without progression will be censored at the date of last tumor assessment.

Objective response rate is defined as the proportion of subjects with best overall response of CR (complete response) or PR (partial response).

Clinical benefit rate (CBR): is defined as the proportion of subjects with best overall response of CR (complete response) or PR (partial response) or with stable disease (SD) for at least 24 weeks.

Duration of overall response: The duration of overall response is measured from the time measurement criteria are met for CR or PR (whichever is first recorded) until the first date that recurrent or progressive disease is objectively documented (taking as reference for PD the smallest measurements recorded since the treatment started).

Duration of overall CR is measured from the time measurement criteria are first met for CR until the first date that progressive disease is objectively documented.

Duration of stable disease: Stable disease is measured from the start of the treatment until the criteria for progression are met, taking as reference the smallest measurements recorded since the treatment started, including the baseline measurements.

## 6. SAFETY MEASUREMENTS

Safety is to be evaluated by

- Adverse events
- Clinical laboratory tests,
- Physical examination findings,
- Vital signs measurements,

The following sections include details and definitions for the safety measurements to be summarized per list of TLFs included in Appendix 1.

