The most common laboratory abnormalities (incidence \geq 50%) were anemia, hypercholesterolemia, hypertriglyceridemia, hyperglycemia, lymphopenia, and increased creatinine. The most common grade 3/4 laboratory abnormalities (incidence \geq 3%) were lymphopenia, hyperglycemia, anemia, hypophosphatemia, and hypercholesterolemia. Deaths due to acute respiratory failure (0.7%), infection (0.7%), and acute renal failure (0.4%) were observed on the everolimus arm. The rates of treatment-emergent adverse reactions resulting in permanent discontinuation were 7% and 0% for the everolimus and placebo treatment groups, respectively. Safety data from study [C2240] are described in detail in Section 1.4.3.3.

Overall, safety data available from completed, controlled and uncontrolled studies are consistent with the aforementioned findings of the Phase III trial. Everolimus is generally well tolerated at weekly and daily dose schedules. The safety profile is characterized by manageable adverse events (AEs). These AEs are generally reversible and non-cumulative.

Further detailed information regarding everolimus clinical development, safety and efficacy is provided in the Investigator's Brochure.

1.4.3.4 Clinical Experience with Everolimus in Metastatic Breast Cancer Resistant to Non-Steroidal Aromatase Inhibitors

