9.2 Safety Analyses

A descriptive comparison of overall toxicity and of grade 3-4 toxicity in the combination arm and the fulvestrant arm will be provided. Assuming 65 patients are treated on each arm, the exact binomial 90% confidence interval on the rate of severe toxicities will be no wider than 22% (+/- 11%). The probabilities of observing a rare toxicity (true rate of 5%) will be 96% on each arm.

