10.1 Collection of Safety Information

Adverse Event (AE) is defined as any new untoward medical occurrence or worsening of a pre-existing medical condition in a patient administered a medicinal product in a clinical investigation and which does not necessarily have a causal relationship with this treatment. An AE can therefore be any unfavorable and unintended sign (including an abnormal laboratory finding, for example), symptom, or disease temporally associated with the use of a product (investigational or marketed), whether or not considered related to the product (investigational or marketed). Abnormal laboratory values or test results constitute adverse events only if they induce clinical signs and symptoms, are considered clinically significant, or require therapy.

Following written consent to participate in the study, all serious AEs should be collected on a patient. The collection of non-serious AE information should begin at initiation of therapy.

All identified AEs must be recorded and described on the appropriate page of the Case Report Form (CRF). If known, the diagnosis of the underlying illness or disorder should be recorded, rather than individual symptoms. The following information should be documented for all AEs: date of onset and resolution, severity of the event; the investigator's opinion of the relationship to investigational product (see definitions below); treatment required for the AE; cause of the event (if known); and information regarding resolution/outcome.

Severity

CTCAE term (AE description) and grade: The descriptions and grading scales found in the revised NCI Common Terminology Criteria for Adverse Events (CTCAE) Version 4.0 will be utilized for AE reporting. A copy of the CTCAE Version 4.0 can be downloaded from the CTEP web site (<http://ctep.cancer.gov>).

All appropriate treatment areas should have access to a copy of the CTEP CTCAE Version 4.0 (see Appendix E).

Attribution

The following categories and definitions of causal relationship or attribution to study drug should be used to assess Adverse Events:

- **Definite:** There is a reasonable causal relationship between the study drug and the event. The event responds to withdrawal of study drug (dechallenge) and recurs with rechallenge, if clinically feasible.
- **Probable:** There is a reasonable causal relationship between the study drug and the event. The event responds to dechallenge. Rechallenge is not required.

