## **7.8. Safety Analysis**

### **7.8.1. Adverse Events**

Adverse events (AEs) will be graded using CTC Version 4, coded using MedDRA dictionary version 16.0, and flagged as treatment emergent if start date of the adverse event is on or after Cycle 1 Day 1 dosing. For adverse events with partial start date (i.e., with only month and year are recorded), the following imputation rule will be applied: 15th of the month or first dose date, whichever comes later.

All AEs and treatment-related AEs will be summarized for all treated subjects by toxicity grade and by treatment arm.

AEs with relationship reported as 'Definite', 'probable' and 'possible' are considered study drug related. AEs with relationship reported 'not likely' and 'not related' are considered not study drug-related. AEs with missing relationship will be considered study drug related.

The following by subject data listings will be prepared: subjects with serious adverse events, subjects with Grade 5 adverse events, and subjects with second primary cancer.

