## 11. APPENDIX 1: LIST OF TABLES, LISTINGS AND FIGURES REQUESTED FOR PUBLICATION

*The following list of required TLFs was provided by PrECOG on 24 May 2013.*

PrE0102 Tables, Listings, Figures  
5/24/13

Table (1): Accrual by Institution

Table (2): Case Status (by arm and total):

Number Enrolled  
Number Ineligible  
Number Withdrawn before Treatment  
Eligible and Treated

Listing (1): Reasons ineligible

Listing (2): Reasons for not starting treatment

Table (3) of Stratification Factors (by arm and total)

Cross-tab (4) of Stratification Factors and Corresponding data from CRF (by arm and total)

Table (5): Subject Characteristics at Study Entry (by arm and total)

Table (6): Number Cycles of Treatment Received by Reason off Treatment (by arm)

Table (7): Dosing: Median and range dose during induction and continuation (by arm and agent)

Toxicity Tables (include all subjects receiving at least 1 dose of study drug/placebo. Count each subject once at the highest grade):

(8) All events, grade 1 to 5, regardless of attribution, by arm and grade

Count

Percent

(9) Treatment-related events, grade 1 to 5, by arm and grade

Count

Percent

Above 2 tables should use CTCAE terminology if possible

(10, 11) Same 2 tables, by System Organ Class rather than individual event

Listing (3) of Serious Adverse Events

Listing (4) of Subjects with Grade 5 Adverse Events

Table (12) of Best Overall Response, by response category and treatment arm, including unevaluable subjects as non-responders

Table (13): Objective Response rate and 90% exact binomial confidence interval, by arm, and Clinical Benefit Rate (CR+PR+SD) with 90% exact binomial confidence interval, by arm and both overall

List (5) of Subjects Unevaluable for Response, with arm and reason

Listing (6) of Second Primary Cancers

Table (14) showing PFS, TTP and OS: Median and 90% CI, or 2-year rates with 90% CI

Listing (7) of Bone Modifying Medications

Figure 1 – PFS by treatment arm

Figure 2 – OS by treatment arm

An additional listing for Bone Modifying Medication was requested via email on 11Jun2013.

For completeness, an additional table summarizing adverse events was included in TLF templates.

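### Laboratory tests are named as a safety measure but have no planned output, so some grade 3-4 laboratory toxicity may be under-counted, by an amount the documents do not allow us to fix

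*SAP*

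**What the plan says.** SAP 6 lists "Clinical laboratory tests" beside adverse events, physical examination and vital signs as the means of evaluating safety. It then ties what is summarised to a list: "The following sections include details and definitions for the safety measurements to be summarized per list of TLFs included in Appendix 1". Its only subsections are 6.1 Adverse Events and 6.2 Concomitant Medications.

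SAP 7.8 has one subsection, 7.8.1, whose summary rule is: "All AEs and treatment-related AEs will be summarized for all treated subjects by toxicity grade and by treatment arm". In Appendix 1, Tables 8 to 11 are AE tables, and the safety listings cover serious AEs, grade 5 AEs and second primary cancers. The one addition to the templates that bears on safety tables is again about AEs: "For completeness, an additional table summarizing adverse events was included in TLF templates".

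Protocol 10.1 decides when a laboratory result enters those tables: "Abnormal laboratory values or test results constitute adverse events only if they induce clinical signs and symptoms, are considered clinically significant, or require therapy". SAP 6.1 repeats the general AE definition, which mentions abnormal laboratory findings, but leaves this limit out.

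Protocol 9.2 states the aim: "A descriptive comparison of overall toxicity and of grade 3-4 toxicity in the combination arm and the fulvestrant arm will be provided". The safety profile is a secondary objective (Protocol 2.2).

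**The concern.** A grade 3-4 laboratory value that causes no symptoms, is not treated and is not judged clinically significant appears in no planned table or listing. Whether it counts depends on how each site judges significance. A reader who has only the SAP would not see this filter, because SAP 6 names laboratory tests and SAP 6.1 describes laboratory findings as AEs without the limit.

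This matters because of the drug's known profile. In the renal cell carcinoma trial summarised in Protocol 1.4.3.3, the laboratory abnormalities seen in at least 50% of patients "were anemia, hypercholesterolemia, hypertriglyceridemia, hyperglycemia, lymphopenia, and increased creatinine". The same section gives five grade 3/4 laboratory abnormalities with incidence of at least 3%: lymphopenia, hyperglycemia, anemia, hypophosphatemia and hypercholesterolemia. If part of this is missed, the grade 3-4 comparison between arms is incomplete, and the publication would give no sign of it.

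**Working it through.** **Step 1. Which values are exposed.** The five grade 3/4 abnormalities of Protocol 1.4.3.3, set against the protocol's own responses:

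| Abnormality | Response in the protocol | Likely route to an AE under 10.1 |
|---|---|---|
| Hypercholesterolemia | 5.3.2.7: treatment advised from grade 2 | Therapy, if managed per protocol |
| Anemia | Table 5-2: interruption at grade 3 and 4 | Probably judged significant, though the protocol does not say so |
| Hyperglycemia | 5.3.2.7: monitoring, and control before starting; no on-study threshold by grade. Exempt from the grade 3 row of Table 5-1 | Therapy if given, otherwise judgement |
| Lymphopenia | Not named in Table 5-2. Grade 3-4 hematologic toxicity triggers repeat blood counts (Section 7, note d) | Judgement; repeat testing is not itself a route |
| Hypophosphatemia | 5.3.2: electrolytes to be monitored; no row of its own | Therapy if given, otherwise judgement |

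Grade 3-4 AST/ALT, neutropenia and thrombocytopenia also call for interruption (Tables 5-1 and 5-2), so they resemble anemia. The general rows of Table 5-1 (grade 3 AE, any other grade 4) do not settle the last three lines. That table covers suspected drug-related AEs, so it presupposes that the value has already been classed as one.

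**Step 2. The plan's own figures.** Inputs from Protocol 9.2: 65 treated per arm, true rate 5%.

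- Chance of at least one case: 1 − 0.95^65 = 0.964. The protocol states 96%.
- Widest exact 90% interval for 65 patients: 21.6 percentage points, at 33 of 65. The protocol states no wider than 22%.

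Both reproduce. The 96% takes every affected patient as counted.

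**Step 3. Incomplete capture.** Let c be the share of patients with a given grade 3-4 laboratory value in whom it is recorded as an AE. The documents give no value for c; 25% to 100% is an assumed range. For a true rate of 5%, the chance of at least one recorded case is 1 − (1 − 0.05c)^65:

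| c (assumed) | Recorded rate | Chance of at least one in 65 |
|---|---|---|
| 100% | 5.00% | 96.4% |
| 75% | 3.75% | 91.7% |
| 50% | 2.50% | 80.7% |
| 25% | 1.25% | 55.9% |

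**Step 4. In patients.** At the documented floor of 3%, 65 × 0.03 = 1.95 patients per arm have a given abnormality. If 25% to 75% go unrecorded, that is 0.5 to 1.5 patients. At 10%, an assumed rate that is not in the documents, 65 × 0.10 = 6.5 patients, of whom 1.6 to 4.9 would be missed. One patient is 1/65 = 1.5 percentage points.

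**Step 5. Effect on the comparison.** If c is the same in both arms, a true difference d is recorded as c × d. Assumed rates of 20% and 5% differ by 15 points; these would appear as 11.25 points at c = 75%, 7.5 at 50% and 3.75 at 25%.

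**The case against.** The case on the other side is substantial.

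- **Scope.** The SAP is abbreviated and written for a publication (SAP 2.1), and its own sentence limits summaries to the Appendix 1 list. Physical examination and vital signs have no table either. The separate template document was not available for this review.
- **The promise.** Protocol 9.2 does not promise grading from laboratory values. Tables 8 to 11 do give a comparison by arm and grade.
- **Precedent.** Protocol 1.4.3.4 summarises a phase 3 trial of everolimus with exemestane in this disease. There, anemia (6% against under 1%) and hyperglycemia (4% against under 1%) were among the commonest grade 3-4 adverse events, so AE reporting can capture laboratory toxicity and separate the arms.
- **Blinding.** Site staff are blinded during Induction (Protocol 8.1.3.4), so significance is judged without formal knowledge of arm.

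These points reduce the likely size, and the precedent makes substantial loss of anemia less likely. They do not give an unrecorded lymphopenia or phosphate value a place in any output. Blinding argues against a bias in favour of one arm, but not against the shrinkage in Step 5. SAP 7.1 says that listings will present all data, yet no laboratory listing is named.

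A reader might infer that the protocol keeps every asymptomatic, untreated abnormality out of the AE tables. It does not, because clinical significance is a separate, third route. A reader might also cite lipids as an example, but treatment is advised from grade 2, so a grade 3 value managed per protocol qualifies through therapy. Nor do the separate lists in Protocol 1.4.3.3 prove that AE forms miss laboratory toxicity. They show that one renal cell trial reported the two separately.

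**Conclusion.** The gap is real but narrower than it first looks. SAP 6 names laboratory tests as a safety measure and no laboratory output follows. Grade 3-4 laboratory values reach the tables only through the three routes of Protocol 10.1, one of which is site judgement. The exposed group is mainly lymphopenia, hypophosphatemia and untreated hyperglycemia. Lipids, anemia, neutropenia, thrombocytopenia and AST/ALT should mostly be captured.

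The supported conclusion is that these values may be under-counted. The documents do not show that they are: with full capture nothing is lost, and no capture rate is given. The figures in Steps 3 to 5 rest on an assumed c, and in part on assumed rates, so they show how sensitive the plan is and do not estimate a loss.

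**What to change.** Add to SAP 7.8 and Appendix 1, as a supplement to Tables 8 to 11, a table by arm of worst post-baseline CTCAE v4.0 grade with shift from baseline, for all treated patients during the Induction Phase. Use every recorded blood count, chemistry, fasting glucose and lipid value, scheduled or not, so that the repeat counts triggered by grade 3-4 hematologic toxicity are included. Keep the AE tables, because Table 9 needs attribution.

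Restrict the table to Induction: in the Continuation Phase, blood counts and chemistry are not required for patients on fulvestrant alone (Protocol 7.1.4), so the arms would not be comparable. Show the number of patients with a post-baseline value for each test. Blood counts and chemistry are scheduled every cycle, but glucose and lipids only about every 12 weeks after Cycle 2 Day 1.

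Carry the limiting sentence of Protocol 10.1 into SAP 6.1.

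The cost is programming time for one derived dataset and one table, with no new tests. It requires that laboratory values are in the database, which the documents do not confirm. If they are not, remove laboratory tests from SAP 6 and state that laboratory toxicity is reported only as investigator-recorded AEs.
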